The secondary objective is to compare the primary and secondary outcomes when stratified by stone size. This will allow us to explore the efficiency between Moses and thulium laser on treating large vs. small stones. Previous literature suggested that stone size was associated with operative time.^{ix} Patients will be separated based on the size of their stones: 3-10 mm or 11-20 mm and then randomized to holmium laser with Moses or thulium laser. Patients will be randomized into the groups by a ratio of 1:1.

Research Design and Methods

This study will be a randomized trial comparing ureteroscopy with laser lithotripsy with the Lumenis® Pulse™ P120H holmium laser system with the Moses technology (holmium laser with moses) versus the Soltive™ SuperPulsed Laser System with the thulium fiber laser technology (thulium laser). The primary objective is to compare the procedural time (minutes). We will keep strict timing from the minute the ureteroscope is inserted into the patient to the time the ureteroscope has been removed. The following information will be collected as secondary outcomes: (1) stone free rate; (2) total operative time (minutes); (3) fragmentation/dusting time (minutes, total time to fragment the stone, including the laser was in use and time of pedal pauses); (4) lasing time (minutes, time the laser was in use, not including pedal pauses); (5) total energy used (kilojoules, kJ); (6) laser efficiency (mm per minute); (7) number of times the laser pedals are pressed (left, right, and total pedal presses); (8) stone analysis; (9) complications; (10) quality of life survey (WISQOL short form) both pre-operatively and post-operatively and (11) physician evaluation of the laser. Physicians will complete a one page survey at the end of the case evaluating the laser (survey included as attachment). A total of 3 clinic visits (i.e., pre-operative visit, the stone surgery, and one post-operative visit) will be needed for this study. Stone parameters (i.e. size, location, Hounsfield units, presence of hydronephrosis, stone volume), demographic information, co-morbidities, and post-operative parameters will be collected from the medical record.

Number of Participants

NCT04963062
Protocol 2021-0695

Approximately 164 patients will be enrolled (see Data Analysis for sample size justification).

Inclusion Criteria

1. Patients at least 18 years of age, and less than 89 years old.

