If the patient is interested in the study, a member of the research team will approach him/her for enrollment. Consent process will be conducted face to face. Participants will be provided a written consent form in person. No waiting time is expected between informing the prospective participant and obtaining the consent.

Consent will take place during patients' pre-operative clinic visit. If patients are interested and there is not enough time to consent the patient in urology clinic, study information will be sent home with the patient and the patient will then be consented before their surgery in a private room (pre-operative room). Pre-operative room provides 1-1 1/2 hours of time. This should be ample time to conduct the consent process before surgery anesthesia.

All information about the study will be provided, and ample time will be made available for the participants to consider participation in the study.

Patient Randomization

Patients will be randomized (ratio 1:1) at the time of enrollment to be treated with either the holmium laser with Moses or the thulium laser. We will use Permuted Block Randomization (stratified by stone size 3 - 10 mm or 11-20 mm) (block size 4).

Study Procedures

1. The study team members review patients' medical record during patients' pre-operative clinic visit to see whether patients meet inclusion/exclusion criteria.
2. If patients meet the inclusion criteria, a study team member who is affiliated with the patient's clinical care (e.g., the surgeon) will initially approach the patients who are scheduled for laser lithotripsy treatment of urinary stones. (i.e., informed that there's a research study they may be eligible for, and asked if they want to learn more about it).
3. If the patient is interested in the study, a member of the research team will approach him/her for enrollment.
4. Patients will be asked to fill out a WISQOL short form at their pre-operative visit. This is standard of care for all stone patients in clinic.

5. Patients' total stone size (pre-operative CT) will be calculated and divided into two groups. Those with stones 3-10 mm and those with stones 11-20 mm. They will then be randomized to either the holmium laser with Moses or the thulium laser (randomization ratio 1:1) group.

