6. Patients will undergo stone surgeries with the laser that they are randomized to. A 200 micron fiber will be used with both machines. The patient's stone(s) will be treated in accordance with our routine clinical practice of fragmenting stone into small pieces (≤ 2 mm). One stone fragment will be collected for stone analysis if the patient does not already have a stone analysis on file (this is also standard of care). The faculty surgeons will perform all surgeries. We are unable to blind the surgeon to the laser used as the laser fibers and laser machines appear and sound different.
7. Procedural time as well as other information (see study design for the detail information) is collected.
8. After surgery, the patients will all have at least an abdominal x-ray within 1 month of surgery, if a CT scan has not already been completed(this is the standard of care). They will also be asked to fill out a WISQOL short form at their one-month follow up appointment. Otherwise, they will continue on our normal postoperative pathway. Postoperative complications will be collected.

Comparison of usual care and study procedures

Compared with our routine care, the only interventions imposed on subjects as a result of this study are (1) pre-procedural randomization to laser lithotripsy with either holmium laser with Moses or thulium laser, and (2) the use of patient & surgery information collected in describing our results. All the other activities are part of our routine clinical practice.

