Since we have 5 surgeons participating in this study, we will use university-based cloud service (such as OneDrive) to temporarily save the enrollment log. Study team member will use their Net ID to access the enrollment log. The enrollment log is completely deidentified. Only participant ID (such as 101, 102) and the laser each participant is randomized to are saved in the enrollment log. Once we complete data collection, we will permanently delete it from the cloud.

Share of results

NCT04963062
Protocol 2021-0695

Some of the information collected for this study will go in the patient's medical record. This includes the results of the one-month post-operative image, stone analysis, stone surgery, and all clinic visits information as these are being conducted as standard of care. All other information from research specific procedures will NOT go in the patient's medical records.

We only publish aggregated results. No individual results will be shared. We will not share the data with outside institutions.

Economic burden to participants

This study does not place financial burden to patients. The study interventions are our routine clinical practice to treat stones. It will be same as they are not involved in this study.

The cost of the two laser treatments are equivalent.

Data Analysis

The data collected will be analyzed as an intention-to-treat analysis. Statistical analyses will include T-test and, if appropriate, Chi-square tests (e.g., for categorical data), and two-way MANOVA. Patient demographics and stone characteristics will be summarized as appropriate as continuous variables (mean and standard deviation) or categorical variables (frequency, percentage). To compare the two groups, continuous variables such as procedural time, total OR time, WISQOL etc., will be analyzed using T test and two-way MANCOVA (stratified by stone size 3 - 10 mm or 11-20 mm). The surgeon will be controlled as a covariate. Categorical variables such as stone free rate will be analyzed using chi-square.

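### The protocol explains why the surgeon cannot be blinded, but describes no masking of patients, WISQOL collectors or stone-free graders

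*Protocol*

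**What the plan says.** Study Procedures item 6 of the protocol makes the only statement about blinding in the available text: "We are unable to blind the surgeon to the laser used as the laser fibers and laser machines appear and sound different". It names the surgeon and nobody else.

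On allocation, the Patient Randomization section says: "Patients will be randomized (ratio 1:1) at the time of enrollment". Enrollment takes place at the pre-operative clinic visit or, failing that, in the pre-operative room (Consent Process). Neither section says whether the patient is told the result.

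Two of the eleven secondary outcomes in Research Design and Methods matter here:

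- **Quality of life.** The outcome is the "quality of life survey (WISQOL short form) both pre-operatively and post-operatively". For the second form, Study Procedures item 8 says: "They will also be asked to fill out a WISQOL short form at their one-month follow up appointment".
- **Stone-free rate.** It comes first in the list: "The following information will be collected as secondary outcomes: (1) stone free rate". Item 8 provides that "the patients will all have at least an abdominal x-ray within 1 month of surgery", unless a CT has already been done. The text gives no definition of stone-free and names no reader.

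On who can see the allocation, Date Management and Confidentiality says of the shared log: "Only participant ID (such as 101, 102) and the laser each participant is randomized to are saved in the enrollment log". Study team members can open that log. Under Share of results, surgery information and the one-month image result both go into the medical record.

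**The concern.** The reason given for not blinding the surgeon is sound, but it does not carry over to the other people whose knowledge of the laser could affect an outcome. A patient under anesthesia does not ordinarily see or hear the machine, and an image read up to a month later can be graded without knowing which laser was used.

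The two outcomes are of the kind that masking protects. WISQOL is self-reported. Stone-free status is a reading of an image, here without a stated definition, so judgement enters. Both are formally compared: stone-free rate by chi-square (protocol, Data Analysis) and the quality-of-life score by MANOVA at a two-tailed 0.05 level (SAP, Data Analysis Plan).

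The Project Summary relies on randomization to reduce bias. Randomization balances the groups at entry. It does not prevent differences in reporting or grading that arise once the allocation is known, and a larger sample does not shrink such differences.

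**Working it through.** **1. The passages side by side**

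| Person | Could learn the laser through | Masking described |
|---|---|---|
| Surgeon | Operating the machine | Stated to be impossible |
| Patient | Allocation at enrollment; conversation with the clinical team | None |
| WISQOL collector | Enrollment log if on the study team; medical record | None |
| Stone-free grader | Medical record; enrollment log if on the study team | None; grader not named |

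**2. Is this only silence?** Not entirely. The section comparing usual care with study procedures lists two departures from routine care, randomization and research use of the data, and says that everything else is routine. Withholding the laser's identity from patients or graders would normally be a departure, and it is not listed. Under the plan as written, nothing keeps the allocation from them.

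**3. Which WISQOL form is exposed?** Study Procedures item 4 (pre-operative form) precedes item 5 (randomization). If that order is followed, only the post-operative form is exposed.

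**4. Is the sample size touched?** The plan's figure first: 4.6 / 6.5 = 0.708 SD. An exact two-sided t-test at 0.05 with 80% power needs 32.33, so 33 per group (power 80.8%), as stated. Then 33 × 1.25 = 41.25, taken as 41, and 41 × 4 laser-by-size cells = 164, or 82 per laser. The calculation concerns procedural time, clocked from scope in to scope out. That outcome is neither patient-reported nor read from an image, so masking patients and graders changes nothing in it.

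**5. Illustration of scale, on assumed values only.** Suppose there is no true difference, 82 patients per laser are analyzed, and the nominal two-sided level is 5%.

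- *WISQOL.* A reporting shift of d SD gives a two-sample t-test (standing in for the planned analysis) a non-centrality of d × √(82/2).
  - d = 0.1: non-centrality 0.64, false-positive chance 9.8%.
  - d = 0.2: non-centrality 1.28, false-positive chance 24.7%.
- *Stone-free rate.* Let grading favor one arm by b = 0.05, so the graded rates are p and p + b, with mean m = p + b/2. Put se0 = √(2m(1−m)/82) and se1 = √([p(1−p) + (p+b)(1−p−b)]/82). The rejection probability is Φ((b − 1.96·se0)/se1) + Φ((−b − 1.96·se0)/se1).
  - p = 0.6: se0 = 0.0756, se1 = 0.0755, giving 10.1%.
  - p = 0.9: se0 = 0.0411, se1 = 0.0410, giving 22.8%.

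With 66 per laser (33 per cell), the ranges become 8.8% to 20.7% for WISQOL and 9.1% to 19.2% for stone-free rate. The documents supply none of d, b or p. These figures show only that small shifts could matter, not that they occur.

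**The case against.** A reader might infer that the trial is open-label by design, with patients told their laser and graders aware of it. The documents do not say so. Item 6 explains one limitation and never declares an open design, and being randomized at enrollment is not the same as being told the result. The consent pages and part of the SAP were not available, so a masking statement there cannot be excluded. This objection stands, and the point is limited to what the available text describes.

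A reader might also assume a strong preference for the newer laser. The support is mixed. Background and Significance calls both lasers new technologies, and Recruitment methods treats either as routine care. On the other side, thulium is newer to this site (Study Intervention) and is hypothesized to shorten procedural time (Study Objectives). An expectation effect is possible but not shown.

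A reader might want the bias as a share of a target WISQOL effect. No such target is given. The only planned effect is 0.71 SD, on procedural time, so any such percentage would have no basis.

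Finally, masking is not entirely free of difficulty. The log and the medical record are shared, and no grader is named. Masking also does not supply the missing definition of stone-free, and it leaves untouched the unblinded surgeon's visual judgement of fragment size. These limits stand, but they do not remove the case for masking the patient and the WISQOL collector, which needs no extra staff or procedure.

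**Conclusion.** The point holds as a low-priority improvement. The available documents describe no masking of patients, WISQOL collectors or stone-free graders, and the reason given for the surgeon does not extend to them. Two secondary outcomes, the post-operative WISQOL and the stone-free rate, are open to bias that could largely be avoided.

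The size of that bias cannot be computed from the documents. The primary outcome and the sample size of 164 are unaffected by this gap.

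The conclusion assumes that the unavailable pages contain no masking procedure, and that anesthesia (type not stated) keeps the patient from identifying the machine.

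**What to change.** - **Patient Randomization and Study Procedures items 6 and 8:** state that the assigned laser is not disclosed to the patient, or to the staff member who collects the one-month WISQOL, until that form is completed.
- **Study Procedures item 8:** state that stone-free status is recorded by existing staff, other than the operating surgeon where feasible, without reference to the enrollment log or operative note.
- **If either is judged impractical:** say so, and report the outcome concerned as open-label.

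The cost is a few sentences and some discipline in conversation and record access. Visits, imaging, sample size and clinical care do not change. Masking the grader is cheap only if existing staff can do the grading. The downside is that masking may be imperfect, because surgery information is in the medical record and study team members can open the log.

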UW, Department of Urology only

Background and Significance

The incidence of urinary tract stone disease is increasing. According to the National Health and Nutrition Examination Survey, as of 2012, 10.6% of men and 7.1% of women in the United States are affected by renal stone disease.ⁱ This has led to an increased demand on Urologists for efficient and safe surgical treatment of stone disease. Over the past two decades, ureteroscopy with laser lithotripsy has become the treatment of choice for most ureteral and renal stones globally.ⁱⁱ The holmium laser is considered the gold standard for laser lithotripsy.ⁱⁱⁱ Holmium laser lithotripsy with Moses and the thulium laser are new technologies meant to improve the efficiency of laser lithotripsy. Both are FDA approved treatment modalities for stone disease. Two in vitro studies have compared Moses versus thulium and shown that thulium has higher ablative volumes than the holmium laser with Moses, but no clinical trials have compared the two treatment modalities.^{iv,v} In this study, we are going to conduct a prospective, randomized clinical trial to determine whether there is a difference in procedural time, intraoperative parameters or stone free rate between the Holmium laser with Moses and the thulium laser. This is significant as this may lead to shorter overall operative times, which may result in decreased operative costs and complications.^{vi,vii}

Study Objectives

The primary objective of this study is to compare the procedural time to acceptable stone fragmentation during clinical use of the holmium laser with Moses and the thulium laser. Our hypothesis is that the thulium laser will have decreased procedural time compared to the holmium laser with Moses. Secondary outcomes will include intra-operative parameters and post-operative parameters. Our clinical practice is to treat urinary stones until the stone is reduced to fragments \leq 2 mm in size. This is determined by using the laser fiber (A 200 micron fiber will be used with both groups), to visually estimate the size of the resultant fragments.^{viii}

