Participation in the study will require a pre-operative CT abdomen without contrast, which is standard of care, as well as at least an abdominal x-ray post operatively which is also standard of care. Four surgeon will perform the ureteroscopy (i.e., [name], [name], [name], [name], and [name]). During surgery, patients' stones will be treated in accordance with our routine clinical practice of fragmenting stones into small pieces (<2 mm). Surgeons will use a 200 micron fiber for both the holmium laser with Moses and the thulium laser, but they will have the discretion to switch to a different fiber (ex. 150 micron thulium fiber) if they feel it is necessary during the case (if the surgeon changes the fiber during the surgery, the data will be analyzed separately). A stone fragment will be collected for stone analysis if the patient does not have one on file. This is our standard of care suggested by AUA guideline.^x All patients enrolled will undergo routine post-operative follow up including clinic appointments and imaging evaluation (with at least an abdominal x-ray). An abdominal x-ray is used for follow up of nephrolithiasis and provides significantly less radiation, and it is our routine care. However, if the patient already has a CT completed by the follow-up visit, an x-ray is not needed. WISQOL short form will be administered during the pre-operative appointment and at the post-operative appointment, which is standard practice in our clinic.

Withdrawal of participants

Patients can withdraw anytime. Once they decide to withdraw, they will continue their standard clinical care with us. We will continue to collect patients' information from patients' medical records for their routine medical care.

Study Intervention

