All procedures performed by surgeons who are board-certified. If significant injury or inefficient fragmentation of the stone occurs, the surgeon will have the discretion to transition to a different laser for patient safety reasons (The data will be analyzed as an intention-to-treat analysis). All patients enrolled will undergo routine post-operative follow up including clinic appointments and imaging evaluation. Any complications will be recorded, reported, and treated appropriately.

Regular inquiries of study flow, pertaining to patient recruitment, randomization, and adverse events will be scheduled to occur after the first week and subsequently every two weeks. The lead researcher, [name], will be responsible for the inquiries. Any adverse events will be monitored as per standard protocol in clinical use. A comparison of adverse events between groups (e.g., to determine whether those assigned to the thulium laser group are experiencing more frequent or serious adverse effects) will be included. No significant adverse events are anticipated for the lasers, as they are routinely used in urology practice. Any adverse events or unanticipated problems will be reported to the PI and IRB and treated accordingly. In addition, members of the study team will be performing these procedures and will monitor the patient during treatment for any signs of complications.

Date Management and Confidentiality

All electronic data will be stored on a HIPAA compliant department server which is maintained on password and firewall-protected computers in locked offices of the Department of Urology, located in a security-protected building. Data to be analyzed after extraction. All paper records (such as WISQOL) will be saved in a locked office/cabinets of IRB approved study staff. Only key personnel listed on this study will have access to this information. All data analysis files will be devoid of direct patient identifiers. Direct identifiers will be destroyed at study closure or at the time of publication. De-identified data will be stored for potential future studies that have proper approval.

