We plan to enroll 164 patients in this study. Patients will be stratified into two groups according to their stone size (3-10 mm or 11-20 mm) and then randomized to either holmium laser with Moses or thulium laser. The stone size is defined as the largest stone size (largest diameter on pre-operative CT), if patients have multiple stones. Previous literature suggested stone size is associated with operative time.^{ix} A significance level of 0.05 will be used with a two-sided two-sample equal-variance t-test. Group sample sizes of 33 and 33 achieve 80% power to detect a significant difference between the means when the mean difference is 4.6 minutes with a standard deviation of 6.5 minutes. We also decide to increase the sample size by 25% (41 patients per group). This will allow for the possibility that the randomization scheme is intra-operatively abandoned for some reason (e.g., equipment failure), that the planned procedure was unable to be completed for some reason, as determined by the surgeon in

charge of the case, and/or that the patient – after his/her procedure – wishes to withdraw from the study and exclude his/her information from our analysis.

ⁱ Scales CD Jr, Smith AC, Hanley JM, Saigal CS; Urologic Diseases in America Project. Prevalence of kidney stones in the United States. *Eur Urol*. 2012 Jul;62(1):160-5.

ⁱⁱ Geraghty RM, Jones P, Somani BK. Worldwide Trends of Urinary Stone Disease Treatment Over the Last Two Decades: A Systematic Review. *J Endourol* 2017 Jun;31(6):547-556.

ⁱⁱⁱ Assimos D, Krambeck A, Miller NL, et al: Surgical Management of Stones: American Urological Association/Endourological Society Guideline, PART II. *J. Urol.* 2016.

^{iv} Andreeva V, Vinarov A, Yaroslavsky I, et al. Preclinical comparison of superpulse thulium fiber laser and a holmium:YAG laser for lithotripsy. *World J Urol*. 2020 Feb;38(2):497-503.

^v Ventimiglia E, Doizi S, Kovalenko A, et al. Effect of temporal pulse shape on urinary stone phantom retropulsion rate and ablation efficiency using holmium:YAG and super-pulse thulium fibre lasers. *BJU Int*. 2020 Jul;126(1):159-167.

^{vi} Bagrodia A, Gupta A, Raman JD, et al. Predictors of cost and clinical outcomes of percutaneous nephrolithotomy. *J Urol*. 2009 Aug;182(2):586-90.

^{vii} Schuster TG, Hollenbeck BK, Faerber GJ, Wolf JS Jr. Complications of ureteroscopy: analysis of predictive factors. *J Urol*. 2001 Aug;166(2):538-40.

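### Fibre-change cases are to be analysed separately, although the protocol otherwise commits to intention-to-treat and keeps even laser switches under it

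*Protocol*

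**What the plan says.** Both groups start with a 200 micron fibre. Under Comparison of usual care and study procedures, the protocol gives surgeons "the discretion to switch to a different fiber (ex. 150 micron thulium fiber) if they feel it is necessary during the case", and the parenthesis that follows reads "if the surgeon changes the fiber during the surgery, the data will be analyzed separately".

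Two other places state the analysis principle. The Data Analysis section says "The data collected will be analyzed as an intention-to-treat analysis" and makes no exception for fibre changes. The Safety Monitoring Plan covers the larger departure, in which the surgeon may "transition to a different laser for patient safety reasons (The data will be analyzed as an intention-to-treat analysis".

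Study Procedures, step 6, says of blinding: "We are unable to blind the surgeon to the laser used". Research Design and Methods defines the primary endpoint by "strict timing from the minute the ureteroscope is inserted into the patient to the time the ureteroscope has been removed".

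The SAP's Data Analysis Plan assigns a Wilcoxon test to procedural time. It names no analysis set and does not mention fibre changes. Part of the SAP was not available for this review, so nothing is claimed about that part.

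**The concern.** A change of laser replaces the treatment under study, yet the patient stays under intention-to-treat. A change of fibre is a smaller departure, yet it gets a different rule. Taken at its word, that rule conditions the primary comparison on something that happens after randomisation, at the discretion of someone who knows the allocation.

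Such removal biases the comparison when two things hold together: it differs between the arms, and it is linked to procedural time. Both are possible here. The discretion covers both lasers, but the only example is a thulium fibre. Time spent changing a fibre falls inside the insertion-to-removal interval, and a surgeon may change fibre because a case is going slowly. Losing slow thulium cases would make thulium look faster; losing slow Moses cases would hide part of a real thulium benefit.

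The undefined wording also leaves the analysis set open to choice after the times are known.

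**Working it through.** **1. The rules side by side.**

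| Event during surgery | Stated handling | Protocol section |
|---|---|---|
| Change of laser | Intention-to-treat | Safety Monitoring Plan |
| Change of fibre | Analysed separately | Comparison of usual care and study procedures |
| All data collected | Intention-to-treat, no exception for fibre changes | Data Analysis |

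Two similar events get two different phrases, so the plain reading is that they are handled differently.

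**2. The plan's own figure.** The Data Analysis section gives a difference of 4.6 min, SD 6.5 min, two-sided 0.05, t-test, and 33 per group for 80% power. The noncentral t calculation gives n = 32.3, rounded up to 33, with power 80.8%. Then 33 × 1.25 = 41.25, stated as 41, and 41 × 4 cells (two lasers, two size strata) = 164, or 82 per laser. The figure reproduces, and the SD and arm size can be used below.

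**3. Shift in the mean under an assumed model.** Not in the documents and therefore assumed: the share p removed from an arm, and the correlation ρ between procedural time and the score that drives fibre change. If the p with the highest scores are removed, that arm's mean falls by

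ρ × 6.5 × φ(z) / (1 − p), where z is the upper p point of the standard normal and φ its density.

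For 2, 4 and 8 of 82 removed (2.4%, 4.9%, 9.8%), φ(z)/(1 − p) is 0.0587, 0.1063 and 0.1910. For example, with 8 removed and ρ = 0.5: 0.5 × 6.5 × 0.1910 = 0.62 min. When both arms lose cases, the shift is the difference between the two arms' values.

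**4. Chance of a false result in thulium's favour.** Simulated normal times, 82 per arm, no true difference, two-sided Wilcoxon at 0.05, so nominally 2.5% in this direction.

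| Removed thulium / Moses | Shift (min), ρ = 0.3 | Shift (min), ρ = 0.5 | False 'thulium faster', ρ = 0.3 | ρ = 0.5 |
|---|---|---|---|---|
| 2 / 0 | 0.11 | 0.19 | 3.1% | 3.6% |
| 4 / 0 | 0.21 | 0.35 | 3.7% | 5.3% |
| 8 / 0 | 0.37 | 0.62 | 5.3% | 8.3% |
| 4 / 2 | 0.09 | 0.16 | 2.9% | 3.8% |
| 8 / 4 | 0.17 | 0.28 | 3.7% | 4.9% |
| 8 / 8 | 0 | 0 | 2.6% | 2.6% |

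With ρ = 0, removing 8/0, 8/4 or 8/8 leaves the rate at 2.5 to 2.6%. Repeat runs of this model differ by about 0.2 percentage points.

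**5. The other direction.** Removing 8 Moses cases only, at ρ = 0.5, gives a false 'Moses faster' in 8.4% and a false 'thulium faster' in 0.6%. With a true difference of 4.6 min and 41 per arm (one stratum), removing 4 Moses cases only reduces the estimate to 4.0 min and power to 76%, against 87% with nobody removed. At 82 per arm, power stays at 96% or more.

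**6. Cross-check.** If fibre-change cases simply take m minutes longer than the rest, removing a share f of one arm shifts its mean by f × m. With m = 5: 0.05 × 5 = 0.25 min and 0.10 × 5 = 0.5 min, within the range above. With m = 10 and f = 0.10 the shift is 1.0 min. The documents do not show which value applies.

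**The case against.** The strongest reply is that separate analysis does not mean exclusion. The phrase is a parenthesis in a procedural section, while the Data Analysis section states the governing principle. Read together, they could mean a supplementary analysis on top of intention-to-treat, with no conflict. That reading is possible and cannot be dismissed, but the available text does not state it, and the same change settles the matter either way.

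There is also a clinical reason for a separate look. A 200 micron fibre is fixed for both groups, and Study Objectives says the stopping point of 2 mm or less is judged by eye against the fibre. Another fibre therefore alters both the tool and the gauge. This stands as a reason for a supporting analysis. It does not justify taking randomised patients out of the primary one.

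The intention-to-treat commitment is also less clean than it looks. The sample-size allowance in Data Analysis provides for cases in which the randomisation scheme is abandoned during surgery, which may overlap with laser switches. That is a planning allowance and not an analysis rule; it does not list fibre changes, and the Safety Monitoring Plan is explicit about laser switches.

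Finally, a reader might infer that the rule will favour thulium, because the only example is a thulium fibre. The documents do not support that. The discretion covers both lasers, Study Intervention describes the two fibres as the same size, and no rate is given for either arm. Unequal removal is possible, not shown, and could go either way.

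**Conclusion.** The point holds as an inconsistency that should be resolved before analysis. On the plain reading, fibre-change cases leave the primary comparison through a discretionary, unblinded decision after randomisation, contrary to the protocol's own principle.

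The size is illustrative. With thulium cases only removed and ρ of 0.3 to 0.5, the false-positive chance in thulium's favour rises from 2.5% to about 3 to 5% when 2 to 5% are removed, and to 5 to 8% when 10% are removed, with shifts of about 0.1 to 0.6 min. These shifts are small against the 4.6 min target, and there is essentially no bias if removal is equal between arms or unrelated to time. A reader might go further and conclude that the primary result will be biased or the sample size undermined; neither follows. The stated sample size reproduces, and the rate of fibre changes and their link to time are unknown. Confidence is medium, because the phrase may have been meant as an extra analysis. The main gain is an analysis set fixed in advance.

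**What to change.** Replace the parenthesis under Comparison of usual care and study procedures with: *Cases with a change of fibre stay in the randomised arm for the primary intention-to-treat comparison, as cases with a change of laser do; a supporting analysis without fibre-change cases will be reported.* Put the same sentence in the SAP for the Wilcoxon test of procedural time. Report counts of, and reasons for, fibre and laser changes by randomised arm.

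The cost is a few sentences and one case-record item (fibre or laser change, with reason), and no extra patients. The downside is that some times obtained with a fibre other than 200 micron enter the primary comparison. That fits the stated objective to "compare the procedural time to acceptable stone fragmentation during clinical use", and the supporting analysis still gives the 200 micron comparison. If an additional analysis was all that was meant, the sentence makes that explicit.
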